9.3.1 Efficacy Analyses

The intercurrent event of rescue medication use will be handled using RM=F, i.e., subjects who take rescue medication will be classified as failures for all efficacy assessments that are reported at or after taking rescue medication. The RM=F method will apply to all efficacy endpoints, except the secondary efficacy endpoint of rescue medication use within 24 hours postdose.

9.3.1.1 *Primary Endpoints*

Zavegepant will be tested for superiority against placebo at an $\alpha=0.05$ level for both co-primary endpoints using the efficacy analysis set. For each endpoint, treatment groups will be compared using a Cochran-Mantel Haenszel test to estimate the difference in percentages of subjects achieving the endpoint response criteria (zavegepant – placebo) stratified by prophylactic migraine medication use at randomization (yes or no). The percentage of subjects achieving the endpoint response criteria will be presented with a 95% confidence interval (CI) by treatment group. The difference in percentages between treatment groups will be presented with a 95% CI and p-value.

Subjects with missing data at 2 hours postdose will be classified as failures (i.e., Non-Completer = Failure; NC=F).

Sensitivity analyses will be described in the SAP.

9.3.1.2 *Secondary Endpoints*

If the tests of both co-primary endpoints are significant (i.e., both p-values are ≤ 0.05), then the secondary endpoints will be tested hierarchically at the $\alpha=0.05$ level in the order shown in the Secondary Endpoints section, using the efficacy analysis set. Thus, a secondary endpoint will be tested only if the preceding secondary endpoint in the hierarchy is determined to be significant (i.e., p-value ≤ 0.05). The same statistics will be presented as those for the co-primary endpoints.

For endpoints based on a single time point, such as phonophobia freedom at 2 hours postdose, subjects with missing data at a single time point will also be classified as failures. For endpoints based on multiple time points, such as sustained pain relief from 2 to 48 hours postdose, subjects with missing data at (1) 2, 24, or 48 hours postdose, or (2) more than 1 time point from 3 to 8 hours postdose will also be classified as failures.

9.3.2 *Safety Analyses*

Deaths will be listed without regard to onset for the enrolled analysis set.

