6.1.1.1 Tables

Treatment Group Presentation

Tables present results by treatment group (i.e., zavegepant 10 mg and placebo) with the following exceptions:

- Results for the enrolled analysis set are presented only by overall, without treatment group.
- Results for study population parameters (see Section 6.2) and pre-treatment safety also include overall.

Time-to-event Tables

Time-to-event endpoints are summarized with Kaplan-Meier tables. Refer to the Zavegepant Core SAP for additional details.

Time-to-event distributions of endpoints are tabulated with the following descriptive statistics: number and percentage of subjects with events; number and percentage of subjects censored in or before the last time interval; number and percentage of subjects censored in the last time interval; time-to-event median with 95% CI, first quartile, and third quartile. The 95% CI for the median is estimated using the method of Brookmeyer and Crowley.

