The intercurrent event of rescue medication use is handled using Rescue Medication = Failure (RM=F), i.e., subjects who take rescue medication are classified as failures for all efficacy assessments that are reported at or after taking rescue medication, i.e., (1) rescue medication start date/time \leq eDiary finding date/time if start time is not missing, or (2) rescue medication start date \leq eDiary finding date if start time is missing; see Sections 6.2.6.2 and 7.1). This method applies to all efficacy analyses, except the secondary endpoint of rescue medication use within 24 hours postdose.

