Analyses are based on non-missing, postdose efficacy data relevant to each endpoint.

For a given time-to-event endpoint, subjects are considered to have an event through X hours ($X = 4$ or 8) if the first postdose eDiary finding date/time defining response is (1) at or before the upper bound of the X -hour analysis window in minutes (see Table 5), and (2) is before the imputed rescue medication start date/time, if not missing (see Section 7.1).

Otherwise, subjects who do not have an event through X hours are censored at the earliest of the following: (1) upper bound of the X -hour analysis window + 1 minute; (2) time from the study drug start date/time to the imputed rescue medication start date/time, if the time is at or before the upper bound of the X -hour analysis window in minutes; (3) time from the study drug start date/time to the last non-missing finding date/time defining the endpoint, if the time was before the lower bound of X -hour analysis window in minutes.

For each endpoint listed above, time to event is assessed by treatment group as follows:

- Kaplan-Meier plot and table using the following time intervals postdose: 0 to 15, >15 to 30, > 30 to 45, > 45 to 60, > 60 to 90, > 90 to 120, > 120 to 180, > 180 to 240, > 240 to 360, > 360 to 495, and > 495 minutes. The Kaplan-Meier plot displays the percentage of subjects with the event on the y-axis versus time in minutes on the x-axis.
- Time-to-event distribution table (minutes), including a log-rank p-value (zavegepant versus placebo).

See Section 6.1.1.1 for additional table and plot attributes.

6.3.4.4 *Efficacy Endpoints Compared over Time*

Treatment group comparisons of the percentage of subjects achieving response over time use analogous methods as the main analysis of the co-primary endpoint of pain freedom with NC=F and RM=F (see Section 6.3.2.1) for the efficacy analysis set and the following endpoints:

- Pain freedom
- Pain relief
- MBS freedom
- Return to normal function for subjects with functional disability at the time of dosing
- Phonophobia freedom for subjects with phonophobia present at the time of dosing
- Photophobia freedom for subjects with photophobia present at the time of dosing

- Nausea freedom for subjects with nausea present at the time of dosing.

For each endpoint and time point from 15 minutes through 48 hours postdose, the following are presented:

- Response rate (i.e., “n/N” and percentage), ASE, and 95% CI for each treatment group

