7 CONVENTIONS

7.1 Derived Dates

Derived dates are defined as follows:

- Study drug start date/time: Earliest (1) study medication dose date and time from the eDiary Migraine Report, or (2) study medication intake date and time from the Study Medication Intake Report (see Section 7.5.1). This date is used to define analysis periods.
- Rescue medication start date/time: Earliest rescue medication date/time (see Section 6.2.6.2). Missing time is considered to be earlier than non-missing time on the same date.
- Imputed rescue medication start date/time: This is used only for time-to-event efficacy analyses in Section 6.3.4.3, and not for time to rescue medication use analyses in Section 6.3.3.8.
 - If the rescue medication start date and time are both not missing, then the imputed rescue medication start date/time is set to the rescue medication start date/time.
 - If the rescue medication start time is missing and the rescue medication start date is equal to the study drug start date, then the imputed rescue medication start date/time is set to the study drug start date/time.
 - Otherwise, if the rescue medication start time is missing and the rescue medication start date is equal to a postdose eDiary finding date with non-missing efficacy data, then the

imputed rescue medication start date/time is set to the first eDiary finding date/time corresponding to non-missing efficacy data.

- Otherwise, if the rescue medication start time is missing and rescue medication start date is equal to the study drug start date + 1 day, then the imputed rescue medication start date/time is set to the study drug start date/time + upper bound of the X -hour analysis window (see Table 5).
- COVID-19 visit date: (1) Complete visit date, if it exists; (2) otherwise, complete date the visit was planned to occur for a missed visit (see Section 9.1.1).
- Last contact date: (1) Earliest complete death date from AE CRFs, if it exists; (2) otherwise, the maximum complete date of the following: AE start or stop; COVID-19 visit only for in-person or remote visits; ECG; eDiary finding; eDiary study drug start; informed consent; IWRS randomization; laboratory collection; nasal inspection; non-study medication start or stop; physical measurement; procedure; rating scale; questionnaire; vital sign; visit. If the last contact date is after the most recent raw database creation date, then it is set to the most recent raw database creation date.

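### Nine exploratory time-to-event analyses censor rescued non-responders at rescue, against the plan's own rescue-equals-failure rule, and SAP 6.3.4.3 declares no exception

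*SAP*

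**What the plan says.** SAP 6.3.4.3 lists nine time-to-event analyses: pain freedom and pain relief through 4 and 8 hours, and MBS freedom, return to normal function, phonophobia, photophobia and nausea freedom through 8 hours.

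- **Event.** The first response must fall within the window, and it counts only if it "is before the imputed rescue medication start date/time, if not missing".
- **Censoring.** Subjects without an event are censored at the earliest of three times. Rule (1) is the window's upper bound plus 1 minute. Rule (2), for rescue, reads "time from the study drug start date/time to the imputed rescue medication start date/time, if the time is at or before the upper bound"; the bound meant is that of the X-hour window. Rule (3) is the last non-missing finding, if that is before the window's lower bound.
- **Plot.** "The Kaplan-Meier plot displays the percentage of subjects with the event on the y-axis versus time in minutes on the x-axis".
- **Table.** SAP 6.1.1.1 asks for "number and percentage of subjects with events; number and percentage of subjects censored in or before the last time interval", with the median and quartiles. SAP 6.3.4.3 adds a log-rank p-value.
- **Untimed rescue.** Under SAP 7.1, if the time is missing and the rescue date "is equal to the study drug start date, then the imputed rescue medication start date/time is set to the study drug start date/time".

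The general rule is in SAP 6.3: "subjects who take rescue medication are classified as failures for all efficacy assessments that are reported at or after taking rescue medication". On its reach: "This method applies to all efficacy analyses, except the secondary endpoint of rescue medication use within 24 hours postdose". Protocol 9.3.1 agrees: "The RM=F method will apply to all efficacy endpoints, except the secondary efficacy endpoint of rescue medication use within 24 hours postdose". SAP 3.2 and 3.2.3 set a composite strategy for efficacy objectives, exploratory ones included. Table 3 has no row for time-to-event endpoints.

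**The concern.** The event definition follows the rescue-equals-failure rule; the censoring does not. Under 6.3 a subject who takes rescue without having responded is a failure from then on. Under rule (2) the same subject leaves the risk set, and Kaplan-Meier treats that subject as still able to respond at the rate seen in those who did not rescue.

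The consequences would be:

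- At the end of the window, curve and table can give two different numbers under nearly the same description.
- A median can be reported although fewer than half the subjects had an event.
- A benefit that works only by preventing rescue is invisible to the curve and the log-rank test.
- Subjects with untimed same-day rescue leave the risk set at time zero but stay in the table's denominator.

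**Working it through.** **Plan figures.** The plan states no figure for these analyses. From SAP section 5 I take 630 per arm and the 2-hour pain-freedom rates of 22.8% and 15.5%. The powers stated there (about 91%, 88% and 80%) reproduce as 91.0%, 87.6% and 79.6%, but nothing below depends on them.

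**Direction.** With S the Kaplan-Meier estimate and N subjects, at the end of the window:

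(1 − KM) − events/N = (1/N) × Σ [S(c) − S(end)] / S(c), summed over all subjects censored early, at time c.

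No term is negative. The sum covers subjects censored by rule (2) and by rule (3); it reduces to rescue alone only if rule (3) censors nobody. In 3,000 random censored data sets the smallest gap was zero to rounding.

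**Hand example (assumed).** Of 100 subjects, 20 respond by 2 h, 30 rescue before 3 h, and 10 of the other 50 respond by 8 h.

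- Table: (20 + 10)/100 = 30%.
- Curve: 1 − 0.80 × (1 − 10/50) = 36%.
- Excess: 30 × 10/50 = 6 subjects.

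**Case A.** Assumptions: 22.8% and 15.5% taken as cumulative response by 2 h; response among those at risk at 3, 4, 6 and 8 h of 14, 14, 18, 18% (active) and 10, 10, 14, 14% (placebo); 8% and 11% of remaining non-responders rescue per interval, independently of later response; no missing data.

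- Curve, active: 1 − 0.772 × 0.86² × 0.82² = 61.6%. Placebo: 1 − 0.845 × 0.90² × 0.86² = 49.4%.
- Events, active: the first interval adds 77.2 × 0.92 × 0.14 = 9.9 points. Continuing, 22.8 + 9.9 + 7.9 + 8.0 + 6.0, about 54.7% unrounded. Placebo: 15.5 + 7.5 + 6.0 + 6.8 + 5.2 = 41.0%.
- Treatment gap: 12.2 points on the curves, 13.7 in the table.

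**Share due to rule (3).** Add an assumed 3% diary loss per interval, after rescue, to the active arm. The curve stays at 61.6% and events fall to 52.5%. The excess is 9.1 points: about 6.8 from rescue and 2.3 from rule (3).

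**Untimed same-day rescue (assumed 2% per arm).** The curve is unchanged and events are multiplied by 0.98. At 8 h the active excess is 61.6 − 53.6 = 8.0 points and the placebo excess is 9.2. At 2 h it is already 22.8 × 0.02 = 0.5 and 15.5 × 0.02 = 0.3.

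**Grid (assumed, no missing data).** Response by 2 h of 15.5, 22.8, 35 or 50%; 6, 10, 15 or 20% response per later visit; 5, 10 or 15% rescue per interval. This gives 48 scenarios, with 7% to 37% rescued by 8 h.

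| Horizon | Excess (points) | Median |
|---|---|---|
| 4 h | 0.4 to 6.3 | 2.0 |
| 8 h | 1.3 to 14.6 | 5.2 |

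In 3 of the 18 scenarios with under 50% events, the curve still reaches 50%, so a median would be reported.

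**Effect on the comparison.**

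- In 180 assumed scenarios with the 22.8% and 15.5% rates and less rescue on active, rule (2) shrank the 8-hour gap in 130 (median change −0.7 points).
- Widening appears in case B: same 2-hour rates; later response 20, 20, 24, 24% against 5, 5, 7, 7%; rescue 12% against 14% per interval. The gap goes from 31.2 (table) to 37.4 points (curve). That is extreme beside the 7.3-point difference at 2 h (22.8 − 15.5).
- In case C response is identical in both arms (18% by 2 h, 12% per visit) and rescue is 5% against 15% per interval. Both curves reach 50.8%, while 47.2% and 40.8% had an event.
- Simulated unstratified log-rank at 630 per arm: in case A the mean z is about 4.4 under rule (2) and 4.9 with the replacement below. In case C it is about 0 against about 2, with nominal p < 0.05 in about 5% against roughly half of trials.

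**The case against.** The strongest reply is that this is a deliberate, pre-specified choice. Section 6.3.4.3 writes its own event and censoring rules, and 7.1 builds an imputed rescue time solely for it. Censoring at rescue describes response without rescue, which is a legitimate question. In case C the log-rank test under the alternative rule would signal faster response although response rates were identical and only rescue differed. That argument would stand if the plan declared a different estimand here. It does not: 6.3 names one exception, this is not it, and a specific rule that never says it departs from the general one leaves the two in conflict.

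Several parts of the reply do stand:

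- A reader might credit the whole excess to rescue. Rule (3) also contributes.
- A reader might infer that the method favours the drug. With more rescue on placebo the gap usually shrinks, and widening needed an extreme case.
- A reader might conclude that the final figure is mislabelled. The Core SAP and the mock tables and figures are not available. Reading the plot as one minus Kaplan-Meier is the natural inference for a curve of subjects with the event, but footnotes and final axis wording cannot be judged. The table also reports numbers censored.
- Rescue-as-failure rates by time point, with stratified differences and p-values, are already supplied in 6.3.4.1 and 6.3.4.4. Rescue use within 24 hours is a tested secondary endpoint with its own time-to-event display.

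**Conclusion.** The point holds as an inconsistency with the plan's own rescue rule, confined to nine exploratory analyses. The direction is certain if the plot is one minus Kaplan-Meier: the curve ends at or above the crude percentage with events. The size is not known; about 1 to 15 points at 8 hours rests on assumed rescue and response rates, rescue independent of later response given non-response, and no missing data. Rescue is probably related to prognosis, which would change the size but not the direction.

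The effect arises mainly after 2 hours, because Protocol 5.5 prohibits rescue before then, and from time zero for untimed same-day rescue. A reader might infer that the trial's efficacy conclusions are at risk. The documents do not support that: SAP section 5 and 6.3.4 make these p-values descriptive and outside the hierarchy. The co-primary and secondary tests and the response rates by time point are unaffected. The change should still be made, because these curves and medians can be read as response rates over time.

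**What to change.** Replace censoring rule (2) in SAP 6.3.4.3 with:

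> Subjects who take rescue medication at or before the upper bound of the X-hour analysis window without an earlier event are censored at that upper bound + 1 minute; this overrides rule (3).

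Keep the imputation of untimed same-day rescue. Footnote the residual from rule (3) for subjects without rescue.

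The override matters. In a check on case A with 2% untimed rescue, and with 30% of rescued and 5% of other non-responders stopping the diary, the 8-hour figures were:

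| Quantity | Active | Placebo |
|---|---|---|
| Crude events | 53.5% | 40.1% |
| Curve, current rule | 62.2% | 50.0% |
| Curve, rule (2) deleted only | 55.3% | 42.0% |
| Curve, replacement text | 53.9% | 40.4% |

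Without missing data, the replacement makes curve and table agree exactly.

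If censoring at rescue is intended, the minimum is to name these analyses as an exception to the rescue rule in 6.3 and to label the axis *Kaplan-Meier estimate, censored at rescue*.

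The cost is one clause and a program change. The downside is that displayed late percentages are lower, and medians come later or are not reached.

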6.4 Safety

Safety analyses are based on the safety analysis set by as-treated treatment group (i.e., the actual treatment received). Results for the overall treatment group are also presented in pre-treatment safety summaries.

Safety parameters include deaths, AEs, and the following findings: laboratory tests; vital signs; physical measurements; electrocardiograms (ECGs); procedures; and S-STS.

Analysis periods are pre-treatment and on-treatment (see Section 7.2). Refer to the Zavegepant Core SAP for slotting safety parameters into analysis periods.

Values and changes from baseline in safety findings (e.g., laboratory tests, vital signs and physical measurements, ECGs) and S-STS endpoints are tabulated as continuous variables descriptively at baseline and the end of treatment visit. These analyses are based on observed data without imputation and regardless of rescue medication use. In these tables of safety parameters excluding laboratory tests, if a subject has multiple values in the end of treatment analysis visit window (see Section 7.3), then the last non-missing value measured in the analysis period is used. See Sections 6.4.3.1 and 6.4.4.1 for further handling of ties on the same measurement date or time. Note that a different algorithm is used for selecting a laboratory test value in the end of treatment analysis visit window (see Section 6.4.2.3).

By-subject listings of safety parameters are described in subsections, and identify on-treatment data. In addition, a by-subject listing of procedures is provided for the enrolled analysis set. These listings display study day and treatment day derived from the measurement date relevant to the endpoint.

6.4.1 Adverse Events

AEs are displayed in tables and listings by SOC and PT, unless specified otherwise.

Refer to the Zavegepant Core SAP for AE start date imputation, AE counting rules in frequency tables, definition of treatment-emergent adverse events (TEAEs), definition of AEs related to study drug, AEs of special interest, and AE listing contents.

The following by-subject AE listings are provided for the enrolled analysis set, unless specified otherwise: AEs (displays COVID-19 visit impact code for visits impacted by COVID-19; see Section 9.1.5.2); SAEs; and AEs leading to study drug discontinuation for the safety analysis set. TEAEs are identified.

6.4.1.1 Deaths

Deaths are identified from any the following sources:

- AE CRF with any of the following: PT containing “death”; reported term containing “death”; outcome of fatal; “yes” response to the question “Did the AE result in death?”; non-missing death date.
- Study Exit Status CRF with early termination reason of death.

Deaths are tabulated by analysis period for the enrolled analysis set as follows: by treatment group for subjects treated with study drug (i.e., those in the safety analysis set); not treated with study drug; and overall. Counts are displayed without percentages.

A by-subject listing of deaths is provided for the enrolled analysis set, and displays all CRF sources of death, safety analysis period, death date (see Section 7.1), study day derived from the death date, treatment day derived from the death date, and the following AE parameters: non-imputed start date; end date; SOC; PT; verbatim term; outcome; and response to the question “Did the AE result in death?”. Refer to the Zavegepant Core SAP for additional details.

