The S-STs is a prospective clinician administered rating scale that contains questions that track both treatment-emergent suicidal ideation and behaviors^{13,14}. The S-STs will be completed on a paper form at the site. At the screening visit, the recall period for completing the S-STs is within the last 30 days prior to the screening visit; at all other visits, the recall period for completing the S-STs is since the last visit (reference [Table 1](#)). Subjects who have a S-STs score of >0 should be evaluated by the Investigator. If the Investigator determines that a subject is at risk of suicide or self-harm, appropriate measures to ensure the subject's safety and obtain mental health evaluation must be implemented. In such circumstances, the subject must immediately be discontinued from the study. The event should be recorded as either an AE or SAE as determined by the investigator and reported within 24 hours to the Sponsor.

6.4 **Efficacy Assessments**

6.4.1 ***Pain***

Subjects record their headache pain intensity using a 4-point numeric rating scale (none, mild, moderate, severe) in the eCOA handheld device at the time points indicated in [Table 1](#).

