6.4.4 Electrocardiogram

ECG parameters include RR, QRS, PR, QT, QTcF, and ventricular heart rate, which are measured with both date and time by the external source CCI

A by-subject listing of ECG results is provided for the enrolled analysis set, and displays COVID-19 visit impact code for visits impacted by COVID-19 (see Section 9.1.5.2).

6.4.4.1 *ECG Changes from Baseline*

Values and changes from baseline in ECG parameters are tabulated as continuous variables at baseline and the end of treatment visit.

If there are multiple values on the same measurement date and time, then the value with the last ECG reference identifier is used.

6.4.4.2 *ECG Interpretation Shifts from Baseline to Worst Category*

ECG interpretation shifts from baseline to the worst on-treatment category are tabulated as the number and percentage of subjects with normal, abnormal, and clinically significant abnormal interpretations.

6.4.4.3 *ECG Abnormalities*

On-treatment ECG abnormalities are tabulated as the number and percentage of subjects in the categories specified in the Zavegepant Core SAP.

6.4.5 **S-STS**

The S-STS is a prospective rating scale that contains 16 patient-reported questions and 6 clinician-reported questions to track both treatment-emergent suicidal ideation and behaviors. Refer to the Zavegepant Core SAP for calculation of the S-STS ideation subscale, behavior subscale, and total scores.

Values and changes from baseline in the self-reported S-STS ideation subscale, behavior subscale, and total score are tabulated as continuous variables at baseline and the end of treatment visit. The number and percentage of subjects in each change from baseline category (i.e., < -1, -1, no change, 1, > 1) are also presented for the ideation subscale, behavior subscale, and total score.

A by-subject listing of S-STS is provided for the enrolled analysis set, and displays COVID-19 visit impact code for visits impacted by COVID-19 (see Section 9.1.5.2).

Refer to the Zavegepant Core SAP for the listing contents.

6.4.6 **Safety Narratives**

A by-subject listing of safety narrative subject identifiers is provided for the following select events and analysis sets as columns:

- All deaths for the enrolled analysis set
- On-treatment SAEs for the safety analysis set treated with zavegepant
- All AEs leading to discontinuation of study drug for the safety analysis set treated with zavegepant

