- Death date: Last contact date derived only for subjects who died (see Section 6.4.1).

No date imputations are performed on these derived dates. Complete dates are those with valid, non-missing day, month, and year.

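### SAP 6.4.1.1 lets the word 'death' in an adverse event term count as a death by itself, and no stated rule removes a false match

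*SAP*

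**What the plan says.** SAP 6.4.1.1 opens its rule with "Deaths are identified from any the following sources". There are two sources: the AE form and the Study Exit Status form. For the AE form the rule reads "AE CRF with any of the following: PT containing “death”; reported term containing “death”; outcome of fatal", followed by a positive answer on whether the event resulted in death and by the presence of a death date. For the exit form it is an early termination reason of death.

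The result is used in four places:

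- **Table (SAP 6.4.1.1):** "Deaths are tabulated by analysis period for the enrolled analysis set as follows", by treatment group for treated subjects, for untreated subjects and overall, as counts without percentages.
- **Listing (SAP 6.4.1.1):** every source that identified the death, the derived death date with its study and treatment day, the verbatim term, the outcome and the answer on whether the event resulted in death.
- **Derived date (SAP 7.1):** "Death date: Last contact date derived only for subjects who died", with a reference back to Section 6.4.1. Last contact is the earliest complete AE-form death date if there is one, and otherwise the latest complete date among a long list of contacts.
- **Narratives (SAP 6.4.6):** the first selection is "All deaths for the enrolled analysis set".

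**The concern.** Four of the six criteria record that the subject died: the fatal outcome, the positive answer, the death date and the exit reason. The two text criteria record only that a word appears. Joining all six by 'any' gives a word match the same force as a recorded death.

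Two kinds of non-fatal verbatim could match. Under Protocol 6.3.5, when the investigator judges a subject to be at risk of suicide or self-harm after a positive S-STS score, "The event should be recorded as either an AE or SAE as determined by the investigator"; that verbatim could mention thoughts of death. A grief reaction could be reported with the bereavement named in the term.

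The deaths count is a headline safety result and is expected to be very low in a single-dose migraine trial. A false entry would make the table, the listing, the derived date and the narrative list wrong together, and in a specific arm if the subject was treated.

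**Working it through.** The plan gives no figure to reproduce here. The check applies the rule to one example and follows it through. The example is hypothetical: a treated subject whose AE reported term includes the words 'thoughts of death', who is alive at the end of the study, with all fatal fields negative.

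| Criterion in SAP 6.4.1.1 | Result |
|---|---|
| Preferred term contains 'death' | depends on coding |
| Reported term contains 'death' | true |
| AE outcome fatal | false |
| AE recorded as resulting in death | false |
| Death date present | false |
| Study exit reason of death | false |
| **Any of the above** | **true: counted as 1 death** |

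**Death date.** The AE form has no death date, so the first branch of last contact in SAP 7.1 does not apply. The second branch returns the latest complete contact date, typically the end of treatment visit or a later record. The living subject therefore has a death date, and the listing derives a study day and a treatment day from it.

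**Table and narratives.** The subject adds 1 to the as-treated arm and 1 to the overall count, and goes on the narrative list. A grief reaction naming a relative's death gives the same trace.

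**With confirmation required.** If a text match also needed one of the four fatal fields, or a resolved query confirming the death, the count for both examples would be 0.

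**Scale.** Protocol 1.2.2.3 reports no deaths in study BHV3500-201, and Protocol 1.3.2 gives 1,588 treated subjects there. Against that, one false match could move the present trial from 0 to 0 + 1 = 1. How many such terms will be reported cannot be derived from either document.

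**How the SAP treats similar searches.** In SAP 6.4.6 a substring search on preferred terms selects hepatic narratives, where a false match costs one unneeded narrative. In SAP 9.2 most medical history deviations are chosen by the medical lead or a designee from a reviewed list of terms. Only in 6.4.1.1 does an unreviewed text match decide a death count.

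**The case against.** A broad search across several fields is a defensible way to avoid missing a death, and several parts of the plan make a false match unlikely or visible.

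- **Few eligible events.** Protocol 5.3 excludes a positive S-STS score, a major depressive episode within 12 months and several psychiatric diagnoses. Protocol 8 asks for a diagnosis, where one is identified, instead of its symptoms. Protocol 8.2.1.1 limits non-serious AE collection to the period from the Baseline Visit to the EOT Visit. A relative's death is not itself an adverse event in the subject.
- **Visible in the output.** The deaths listing would show a non-fatal outcome and a negative answer beside the term. SAP 2.3 provides for draft outputs with dummy treatment groups before lock, so a false entry could be seen while the study is still blinded.
- **A document not seen.** SAP 6.4.1.1 refers to the Zavegepant Core SAP for additional details, which could include a confirmation step.

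Much of this stands, and it limits the point. A reader might infer that every positive S-STS score must be recorded as an AE. Protocol 6.3.5 does not say so: a positive score leads to evaluation, and recording follows only when the investigator finds a risk of suicide or self-harm. A reader might also add fetal death as a likely match, but Protocol 8.1.6 sends pregnancy outcomes to the Pregnancy Report Form, while the text search reads the AE form.

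What the objection does not supply is a rule that takes a false match out of the table. Visibility in a listing is not an exclusion. A programmer following the SAP would have to leave the subject in, and removing the subject would be an unplanned departure. The Core SAP reference closes the paragraph on the listing, and the identification rule above it is stated without qualification. Sensitivity can be kept without letting the text match decide the count.

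**Conclusion.** The point holds as a minor defect in a stated rule. As written, a term mentioning death is sufficient to classify a subject as dead and to assign a death date equal to last contact. The size is one false death per matching non-fatal term.

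The conclusion rests on a literal reading of SAP 6.4.1.1 and 7.1 and on there being no confirmation step in the Core SAP, which was not available. The example terms are illustrations; neither document reports such an event.

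The stronger conclusion, that the trial is likely to report living subjects as dead, is not supported. The frequency is unknown and probably low, and the listing gives a real chance of catching an error before lock. No efficacy result, type I error rate or decision rule depends on this count.

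**What to change.** In SAP 6.4.1.1, remove the two text criteria from the sources that establish a death and make them a trigger: any preferred or reported term containing the word raises a data query or a blinded medical review, to be resolved before database lock. Tabulate and list a death, derive a death date and select a narrative only when at least one of these confirms it: a fatal outcome, a positive answer that the event resulted in death, a death date, a study exit reason of death, or the resolved query. The reference in SAP 7.1 to subjects who died then points to the confirmed definition without further change. If the Core SAP already contains such a step, a cross-reference in 6.4.1.1 is enough.

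The cost is about one sentence in the SAP, one changed condition in the program and a few queries to resolve before lock. A true death with every fatal field left blank would be counted only if its query is answered in time. Because the search is kept, such a case would still be flagged whenever the term itself mentions death.
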